4.6.1 Sensitivity analyses

Competing risk of death

To take into account the possibility of a competing risk of death, a Fine and Gray[3] proportional sub-distribution hazards regression model will be used to take into account the competing risk of death to provide reassurance about the robustness of the analysis. The effect of the randomised intervention will be presented by the sub-distribution hazard ratio and 95% confidence interval. The cumulative incidence function (CIF) obtained from the Fine-Gray model will be plotted separately for each intervention; the median time to event and its 95% CI will be reported by intervention group. The absolute risk difference (and its 95% CI) will also be reported at the median time to event.

Diagnostic position

The analysis of secondary safety outcomes, will consider the occurrence of an event if the diagnostic codes, as defined in Appendix C, occur in any diagnostic position.

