4.5.1 Secondary analyses

The comparison between the groups is considering differing lengths of the same treatment; this inherently causes the potential violation of the proportional hazards' assumption. Therefore, in a secondary analysis of the primary outcome all-cause mortality at 15 months from date of MI will be compared between groups using a logistic regression model stratifying by country and adjusting for cardiac history. Results will be presented as an adjusted odds ratio with corresponding 95% CI and p-value.

² Note that we will not censor at date of withdrawal, as we will not have outcome data collected up to the point of withdrawal and therefore withdrawn participants will be excluded from the analysis.

³ The protocol refers to stratifying by centre but due recruitment being halted early and the potential for small number of outcome events per centre, the analysis will only adjust for country and the effect of centre will be explored in a sensitivity analysis.

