4.5.2 Sensitivity analyses

Two-stage individual participant data (IPD) meta-analysis

In a sensitivity analysis, we will consider a two-stage individual participant data (IPD) meta-analysis[2]. The first stage will analyse the IPD from each country separately as per the analysis model described above in section 4.5. In the second stage, we will combine the individual estimates using a fixed effect inverse-weighted meta-analysis model of adjusted log hazard ratios. The results will be presented as adjusted HRs with 95% confidence intervals for each study and the pooled estimate. A random effects (DerSimonian and Laird method) model will also be estimated to check the robustness of the findings (irrespective of the degree of heterogeneity).

Landmark analysis

Both randomised groups receive the same treatment for the first 3 months and therefore would expect, apart from random chance, to observe no difference in outcomes. In a second sensitivity analysis, we will therefore perform a landmark analysis including only those participants who have survived at 3 months from date of MI. The analysis will be performed as per the analysis model described above in section 4.5

Adjusting for centre

In a third sensitivity analysis, the analysis model specified in section 4.5 will also include stratifying by centre to determine the robustness of the results. In the event of issues with model fitting, this will be performed for Scottish participants only which comprise most randomised participants.

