4.6 Secondary outcomes

The interpretation of trial findings for secondary outcomes will focus on the effect size and 95% CI. No formal adjustment will be made to significance levels to allow for multiplicity.

For each of the following secondary outcomes (appendix C), events are defined as the time to first outcome event during follow-up from date of the index myocardial infarction. Follow-up will be censored at competing causes of death or 15 months from date of MI, whichever occurs first.

Efficacy

- Cardiovascular death and non-fatal myocardial infarction
- Cardiovascular mortality (cardiac and non-cardiac)
- Myocardial infarction (fatal and non-fatal)
- Stent thrombosis
- Coronary revascularisation
- Thrombotic stroke

Safety

- Non-cardiovascular death (including fatal bleeding) and major non-fatal bleeding
- Non-cardiovascular death (including fatal bleeding)
- Major fatal and non-fatal bleeding
- Hospitalisation for bleeding
- Intracranial haemorrhage
- Gastrointestinal bleeding

The analysis will follow that specified for the primary outcome in section 4.5. The number and proportions of participants with an event for individual components of the secondary outcomes will also be reported alongside the composite.

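### SAP 4.6.1 draws its competing-risk curves from a one-coefficient Fine-Gray model, which moves part of any later difference into months 0–3, when both arms have the same treatment

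*SAP*

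**What the plan says.** For the secondary outcomes, SAP 4.6 fixes the time scale: "Follow-up will be censored at competing causes of death or 15 months from date of MI, whichever occurs first". It then carries over the section 4.5 analysis: a Cox model, Kaplan-Meier curves by arm within country, a proportionality check and, on conditions, a time-dependent hazard ratio.

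SAP 4.6.1 adds a sensitivity analysis for competing death, in which "a Fine and Gray[3] proportional sub-distribution hazards regression model will be used". On reporting it says: "The effect of the randomised intervention will be presented by the sub-distribution hazard ratio and 95% confidence interval". On plotting: "The cumulative incidence function (CIF) obtained from the Fine-Gray model will be plotted separately for each intervention". It mentions no proportionality check for this model, no time-varying SHR and no non-parametric cumulative incidence.

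Two other places describe the expected shape of the effect. SAP 4.5.2 gives this reason for its landmark comparison: "Both randomised groups receive the same treatment for the first 3 months and therefore would expect, apart from random chance, to observe no difference". SAP 4.5.1, on comparing two lengths of the same treatment: "this inherently causes the potential violation of the proportional hazards' assumption". The second remark concerns the Cox model for mortality and speaks of a potential violation, but the reason given applies equally to the secondary outcomes.

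**The concern.** With one treatment coefficient, the two Fine-Gray curves are tied together at every time point. They cannot coincide for 3 months and then diverge. If the arms differ overall, the plot must show a difference in months 0–3 and too little new separation in months 3–12.

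When bleeding and ischaemic events diverge is central to a 3 versus 12 month comparison. Protocol 11.6 sets an early, time-varying atherothrombotic risk against a continuous bleeding risk. A reader of these plots could conclude that benefit or harm builds up while both arms are on the same treatment. The Kaplan-Meier curves from 4.5 do not force early separation, but they censor competing deaths and so are not cumulative incidences.

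**Working it through.** SAP 4.6.1 states no figure, so there is none to reproduce. The check asks what the planned curves would show when the truth has no difference before month 3.

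**Inputs from the documents.** Fine-Gray with one arm coefficient (SAP 4.6.1); 15 months from the index MI (SAP 4.6); 1:1 allocation (Protocol 5.5.2); near-zero loss to follow-up (Protocol 9.2); bleeding hazard ratio 0.58 (Protocol 9.2, a meta-analysis figure for ≤6 versus 12 months). For chance error, 4,576/2 = 2,288 UK patients per arm.

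**Assumptions.** The 0.58 acts in months 3–12 only, with a ratio of 1 otherwise. Bleeding rates are as in the table. In rows 1–2 the sub-distribution hazard is constant. In rows 3–4 the bleeding hazard is cause-specific, with competing death at 2% per month to month 3 and 0.8% afterwards.

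**Formulas.** Let F be the true cumulative incidence, f its density and R = 1 − F, with subscripts 12 and 3 for the arms.

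1. The large-sample SHR = exp(β) solves ∫f₃ dt = ∫w(f₁₂ + f₃) dt, where w = SHR·R₃/(SHR·R₃ + R₁₂).
2. The matching baseline is Λ(t) = ∫(f₁₂ + f₃)/(R₁₂ + SHR·R₃).
3. The plotted curves are 1 − exp(−Λ) and 1 − exp(−SHR·Λ), so CIF₃(t) = 1 − (1 − CIF₁₂(t))^SHR.

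**Results** (percentage points; difference = 3-month arm minus 12-month arm; the true month-3 difference is 0 in every row):

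| Assumed bleeding, 12-month arm | SHR | Month 3, Fine-Gray curves (12 v 3) | False gap | Month 15, true | Month 15, Fine-Gray |
|---|---|---|---|---|---|
| Constant, 3% at 15 months | 0.748 | 0.69 v 0.52 | −0.17 | −0.75 | −0.75 |
| Constant, 5% at 15 months | 0.748 | 1.17 v 0.87 | −0.29 | −1.24 | −1.24 |
| Constant 0.5%/month (6.6%) | 0.750 | 1.65 v 1.24 | −0.41 | −1.61 | −1.61 |
| 1.0%/month to month 3, then 0.5% | 0.795 | 3.19 v 2.55 | −0.65 | −1.59 | −1.57 |

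Gaps come from unrounded values.

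**Row 3 in detail.** The true month-3 incidence is the same in both arms: 0.005/0.025 × (1 − exp(−0.075)) = 1.45%. The model replaces it with 1.65% in the 12-month arm and 1 − (1 − 0.0165)^0.75 = 1.24% in the 3-month arm.

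**Months 3–12.** In row 4 the true month-12 difference is −1.61 and the Fine-Gray difference is −1.32. The real separation over these months is 1.61 points, but the plot shows 1.32 − 0.65 = 0.67. About 40% of the plotted 15-month gap (0.65/1.57) appears before treatment differs.

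**Sensitivity.** With the row 4 hazards, hazard ratios of 0.7 and 0.5 give false gaps of 0.45 and 0.79. If the 0.58 persists to month 15, rows 1 and 2 become 0.24 and 0.41. If the hazard ratio is 1, the SHR is 1 and the gap is zero.

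**Chance error.** The standard error of a month-3 difference is √(2p(1 − p)/2,288). For p = 1.45% this is 0.35 points. For rows 1 and 2 it is 0.23 and 0.30.

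**Effect of the fix.** In 400 simulated trials of 2,288 per arm (assumed 5% bleeding, 10% competing death, hazard ratio 0.58 after month 3), the mean month-3 difference was −0.40 (SD 0.15) from Fine-Gray and −0.01 (SD 0.30) from the non-parametric curves.

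**The case against.** The strongest reply is that little rests on this plot. It belongs to a sensitivity analysis of secondary outcomes, and SAP 4.6 says interpretation will centre on effect sizes and confidence intervals. The month-15 values are nearly right. Timing can also be seen elsewhere. Kaplan-Meier curves carry over from 4.5, as does a time-dependent hazard ratio if there is strong evidence of non-proportionality and enough events. The landmark analysis in 4.5.2 arguably carries over too, though 4.6 does not say so. All this stands, and it limits the weight of the point. What remains uncovered is a curve that accounts for competing death without fixing the timing.

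The size is also open to challenge. Protocol 11.6 calls bleeding risk continuous, which favours the constant-hazard rows over the doubled early hazard. The gap is then about 0.2 to 0.4 points. That is below one standard error in rows 1 and 2 and slightly above one in row 3. This stands as well, but the distortion is systematic: it always runs in the direction of the overall effect.

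The wording about plotting separately for each intervention could mean a model stratified by arm, which would avoid the problem. Such a model could not yield the SHR reported in the same paragraph, so the one-coefficient reading is the likelier one.

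A reader might infer more: that every non-fatal secondary outcome will show a false early split, or that the plan leaves timing wholly to these plots. The documents do not support either. Where the SHR is near 1 the curves coincide, and the analyses carried over from 4.5 also address timing.

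**Conclusion.** The point holds as a modest one about presentation. Whenever the estimated SHR differs from 1, the planned curves show separation in months 0–3 that SAP 4.5.2 does not expect, and they understate the separation in months 3–12.

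Under a hazard ratio of 0.58 confined to months 3–12, the false month-3 gap is about 0.2 to 0.4 points with a constant bleeding hazard and 0.65 points with a doubled early hazard. These sizes depend on assumed bleeding and competing-death rates, and on using a meta-analysis ratio as a months 3–12 effect. They are not predictions for this trial.

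The primary outcome is untouched. It would be wrong to conclude that the Fine-Gray analysis misstates the 15-month result: in the scenarios above, its 15-month difference is within 0.02 points of the truth.

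**What to change.** In SAP 4.6.1, replace the model-based plot with the non-parametric (Aalen-Johansen) cumulative incidence by arm, with 95% bands. Take the absolute risk differences from those curves, and keep the Fine-Gray model for the SHR and its confidence interval only.

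This costs one sentence in the SAP and a different plot statement. It needs no new data and leaves the primary analysis unchanged. The downside is that the curves are not adjusted for country or cardiac history and are noisier. In the simulation the SD of the month-3 difference rose from 0.15 to 0.30 points. The extra noise will be most visible for rare outcomes such as stent thrombosis and intracranial haemorrhage, where the bands will show it.

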Appendix C

Outcomes defined used the following codes and positions specified below following the date of index MI unless otherwise specified. If the code is not identified in any admissions/deaths then they will be assumed to not have the outcome of interest.

Data sources

Scotland: SMR00 / SMR01 / NRS Deaths / Prescribing Information System / Scottish Blood Transfusion Database

England: Hospital Episode Statistics / Civil Registrations of Death / Medicines dispensed in Primary Care (NHSBSA data)

Outcome	Code (ICD-10 , OPCS4)
All-cause mortality	Any record of death.
Non-cardiovascular death (including fatal bleeding) and major non-fatal bleeding	
Death due to a non-cardiovascular cause
 
Primary position for cause of death
 
Ax, Bx, Cx, Dx Ex, Fx , Gx , Hx , Jx, Kx , Lx , Mx , Nx , Ox , Px , Qx , Rx , Sx , Tx , Ux , Vx , Xx , Yx , Zx.
 
OR
 
Hospitalisation for bleeding
 
Primary or first secondary position
 
I60x, I61x, I62x, S06.4x, S06.5x, S06.6x, K92.0x, K92.1x, K 92.2x, I85.0x, I98.3x, K22.6x, K25.0x, K25.2x, K25.4x, K25.6x, K26.0x, K26.2x, K26.4x, K26.6x, K27.0x, K27.2x, K27.4x, K27.6x, K28.0x, K28.2x, K28.4x, K28.6x, K29.0x, K62.5x, K66.1x, R58x, I23.0x, I31.2x, I69.0x, I69.1x, I69.2x, H21x, H35.6x, H31.3x, H43.1x, H44.8x, H45.0x, R04.0x, R04.1x, R04.2x, R04.8x, R04.9x, T81.0x, D62x, N83.7x, N93.8x , N93.9x, O03.1x, O03.6x, O04.1x, O04.6x, O05.1x, O05.6x, O06.1x, O06.6x, O20.8x, O20.9x, O46x , O67x, O07.1x, O07.6x, O08.1x, O71.7x , O72.0x , O72.1x , O72.2x , O90.2x , P26.1x , R31x , M25.0x.
 
OR

	
Primary procedure position (OPSC4)
 
E05x , E058x , E059x , F162x , D041x , E203x , F365x , G523x , H212x , H531x , K681x , P093x , P271x , T301x , Y221x , T032x , Y221x , T032x , Y321x , V032x , A052x , A053x , A054x , A103x , A401x , A411x

Non-cardiovascular death (including fatal bleeding)	
Primary cause of death
 
Ax , Bx , Cx , Dx , Ex , Fx , Gx , Hx , Jx , Kx , Lx , Mx , Nx , Ox , Px , Qx , Rx , Sx , Tx , Ux , Vx , Xx , Yx , Zx

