Hospitalisation for bleeding	
Hospitalisation for bleeding
 
Primary or first secondary position
 
I60x, I61x, I62x, S06.4x, S06.5x, S06.6x, K92.0x, K92.1x, K 92.2x, I85.0x, I98.3x, K22.6x, K25.0x, K25.2x, K25.4x, K25.6x, K26.0x, K26.2x, K26.4x, K26.6x, K27.0x, K27.2x, K27.4x, K27.6x, K28.0x, K28.2x, K28.4x, K28.6x, K29.0x, K62.5x, K66.1x, R58x, I23.0x, I31.2x, I69.0x, I69.1x, I69.2x, H21x, H35.6x, H31.3x, H43.1x, H44.8x, H45.0x, R04.0x, R04.1x, R04.2x, R04.8x, R04.9x, T81.0x, D62x, N83.7x, N93.8x , N93.9x, O03.1x, O03.6x, O04.1x, O04.6x, O05.1x, O05.6x, O06.1x, O06.6x, O20.8x, O20.9x, O46x , O67x, O07.1x, O07.6x, O08.1x, O71.7x , O72.0x , O72.1x , O72.2x , O90.2x , P26.1x , R31x , M25.0x.
 
OR
 
Primary procedure position (OPCS4)
 
E05x , E058x , E059x , F162x , D041x , E203x , F365x , G523x , H212x , H531x , K681x , P093x , P271x , T301x , Y221x , T032x , Y221x , T032x , Y321x , V032x , A052x , A053x , A054x , A103x , A401x , A411x

Intracranial haemorrhage	
Intracranial haemorrhage event
 
Primary or first secondary position
 
I60x , I61x , I62x , S06.5x , S06.6x.

	
OR
 
Death due to intracranial haemorrhage
 
Primary cause of death
 
I60x , I61x , I62x , S06.5x , S06.6x.

Gastrointestinal bleeding	
Gastrointestinal bleeding event
 
Primary or first secondary position
 
K92.0x , K92.1x , K 92.2x , I85.0x , I98.3x , K22.6x , K25.0x , K25.2x , K25.4x , K25.6x , K26.0x , K26.2x , K26.4x , K26.6x , K27.0x , K27.2x , K27.4x , K27.6x , K28.0x , K28.2x , K28.4x , K28.6x , K29.0x , K62.5x , K55.2x , K66.1x.
 
OR
 
Death due to Gastrointestinal bleeding
 
Primary cause of death
 
K92.0x , K92.1x , K 92.2x , I85.0x , I98.3x , K22.6x , K25.0x , K25.2x , K25.4x , K25.6x , K26.0x , K26.2x , K26.4x , K26.6x , K27.0x , K27.2x , K27.4x , K27.6x , K28.0x , K28.2x , K28.4x , K28.6x , K29.0x , K62.5x , K55.2x , K66.1x.

Cardiovascular mortality and non-fatal myocardial infarction	
Death due to a cardiovascular cause
 
Primary cause of death
 
Ix
 
OR
 
Myocardial infarction after the Index Admission Discharge Date

	
Primary or first secondary position
 
I21x, I22x

Cardiovascular mortality (cardiac and non-cardiac)	
Death due to a cardiovascular cause
 
Primary cause of death
 
Ix

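### Read literally, the any-position sensitivity analysis in SAP 4.6.1 extends to non-cardiovascular death and would count some cardiovascular deaths as non-cardiovascular

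*SAP*

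**What the plan says.** SAP 4.6.1, under the diagnostic position heading, states its scope as follows: "The analysis of secondary safety outcomes, will consider the occurrence of an event". The criterion is that the Appendix C codes "occur" in any position; in full, the analysis "will consider the occurrence of an event if the diagnostic codes, as defined in Appendix C, occur in any diagnostic position". No outcome is exempted.

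SAP 4.6 lists six safety outcomes. Two rest on non-cardiovascular death: that death alone, and "Non-cardiovascular death (including fatal bleeding) and major non-fatal bleeding".

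Appendix C gives the codes.

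- **Non-cardiovascular death alone.** The position rule is "Primary cause of death". The row holds no hospital diagnosis codes.
- **The composite.** The death part is limited to the primary "position for cause of death", with a code list that begins "Ax, Bx, Cx, Dx Ex, Fx , Gx , Hx" and runs on to Z. The bleeding part uses hospital diagnoses in primary or first secondary position, or a primary procedure code.
- **Cardiovascular mortality.** Any I code as primary cause of death. SAP 4.6 classes it as an efficacy outcome, so the any-position rule does not reach it.

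**The concern.** Searching any position is a reasonable robustness check for a short, specific list such as the bleeding codes: it asks whether bleeds recorded lower down the record change the answer. It does something different when the list is nearly the whole classification. Common comorbidities such as diabetes, kidney disease or lung disease fall under listed letters. If one of them stands as a contributory cause on the record of a death whose primary cause is myocardial infarction, that death meets the relaxed definition of non-cardiovascular death.

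Two things follow. The same death would appear as a safety event in this sensitivity analysis and as a cardiovascular death in the efficacy outcomes. SAP 4.6 also censors at competing causes of death, so it would be both an event and a competing event, with no rule to choose between them. Second, the estimate would become a blend of two effects that the protocol deliberately separates: its objectives and Table 3 set bleeding and non-cardiovascular harm against cardiovascular benefit. The composite inherits the problem through its death part.

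**Working it through.** **1. Which codes are listed.** Comparing A to Z with the Appendix C list for non-cardiovascular death leaves only I and W absent. So any contributory code under the other 24 letters would trigger recounting; an I or W code alone would not.

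**2. The rule applied to one death.** Take primary cause I21 with contributory E11.

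| Analysis | Position rule | Counted as |
|---|---|---|
| Efficacy: cardiovascular mortality | Primary cause | Cardiovascular death |
| Safety, main: non-cardiovascular death | Primary cause | Not an event |
| Safety, 4.6.1 read literally | Any position | Non-cardiovascular death |

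**3. The protocol's own figure.** Protocol 9.2 states 81% power for non-cardiovascular mortality of 6% against 5% with 16,944 patients. A two-proportion calculation with 8,472 per arm, two-sided 5% and no continuity correction gives 81.5%, so the figure is reproduced.

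**4. Inputs for the size.**

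- C = 17.8% cardiovascular and N = 7.6% non-cardiovascular death at one year (Protocol Table 2, Scotland; they sum to the 25.4% all-cause figure).
- Factor 0.667 for consented patients (Protocol 9.2), giving 11.87% and 5.07%.
- True ratio 0.83, the non-cardiac mortality hazard ratio in Protocol 9.2, used only as an illustration.
- Ratio 1.0 for cardiovascular death: an assumption.
- f, the share of cardiovascular deaths with at least one listed contributory code: **not in the documents**, so shown as a range.

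**5. Formulas.**

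- Counted rate = 0.667 × (N + f × C)
- Share cardiovascular by primary cause = f × C / (N + f × C)
- Apparent ratio = (0.83 × N + f × C) / (N + f × C)

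The factor 0.667 cancels from the last two. Example at f = 0.10: N + f × C = 7.6 + 1.78 = 9.38; share = 1.78 / 9.38 = 19%; ratio = (6.308 + 1.78) / 9.38 = 0.86. Example at f = 0.80: 7.6 + 14.24 = 21.84; share = 14.24 / 21.84 = 65%; ratio = (6.308 + 14.24) / 21.84 = 0.94.

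| f (assumed) | Counted rate | Share cardiovascular | Apparent ratio | Share of all deaths counted |
|---|---|---|---|---|
| 0 | 5.1% | 0% | 0.83 | 30% |
| 0.10 | 6.3% | 19% | 0.86 | 37% |
| 0.25 | 8.0% | 37% | 0.89 | 47% |
| 0.50 | 11.0% | 54% | 0.92 | 65% |
| 0.80 | 14.6% | 65% | 0.94 | 86% |

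The last column is (N + f × C) / 25.4.

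At these rates the 4,576 UK patients would have about 232 non-cardiovascular deaths (4,576 × 0.0507). Recounting would add about 54 at f = 0.10 and about 435 at f = 0.80 (4,576 × f × 0.1187).

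**6. Effect on precision.** Adding f × 11.87% to both sides of the protocol's 6% against 5% contrast, still with 8,472 per arm, lowers power from 81.5% to 74% (f = 0.10), 65% (0.25), 53% (0.50) and 45% (0.80). That sample size will not be reached, so this shows only the relative loss.

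The ratios are event-weighted averages of one-year risks, not hazard ratios over the SAP's 15 months.

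**The case against.** The best answer is that diagnostic position was meant for hospital diagnoses only. Most bleeding rows in Appendix C carry a primary or first-secondary limit for hospital codes, while the stand-alone death row speaks of cause of death without the word position. On that reading 4.6.1 loosens only the hospital limit, and non-cardiovascular death stays as it is. The reading is possible, so one cannot say that the sentence can only mean contributory causes. But the SAP nowhere states it. Appendix C uses position for cause of death in the composite row, and the reading leaves the rule with nothing to do for an outcome inside its stated scope.

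It is also fair that Appendix C names the death registries without saying that contributory causes are in the linked extract, and that no definition there uses one. Without them the problem cannot arise. That condition stands.

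A reader might go further and infer three things that the documents do not support.

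- *That the analysis becomes a near copy of all-cause mortality.* It would hold about 37% of all deaths at f = 0.10 and 86% at f = 0.80; which applies is unknown.
- *That it would contradict a sound main result.* With no cardiovascular effect, 0.83 moves to between 0.86 and 0.94: attenuated, in the same direction. Losing the signal altogether would need an adverse cardiovascular effect as well. Protocol 11.6 raises that possibility for 3 months of therapy but gives no size.
- *That any code other than I triggers recounting.* W is also absent from the list.

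**Conclusion.** The point holds as a fault in the wording of one sensitivity analysis. Followed as written, the rule moves some deaths with an I-coded primary cause into a safety outcome defined as non-cardiovascular, and into its composite. For assumed shares from 10% to 80%, and no effect on cardiovascular death, 19% to 65% of the counted events would be cardiovascular by primary cause. A true ratio of 0.83 would appear as about 0.86 to 0.94.

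This rests on three conditions: that the rule is applied literally, that contributory causes are in the linked data, and that the share lies in a range the documents do not supply. It does not follow that the trial's main safety findings are misclassified. The primary endpoint of all-cause mortality and the main secondary analyses, which use primary cause of death, are untouched. The change should still be made, because a robustness check that alters what the outcome means cannot show whether the main result is robust.

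**What to change.** Add one sentence to SAP 4.6.1 saying that the any-position rule applies only to the listed bleeding codes: hospitalisation for bleeding, major bleeding, intracranial haemorrhage, gastrointestinal bleeding, and the bleeding part of the composite. State in the same place that non-cardiovascular death is classified by primary cause of death in every analysis, including the death part of the composite. It would help to say there whether, for fatal bleeding, the rule extends to contributory causes.

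The cost is one or two sentences. No new data are needed, the main analyses do not change, and the intended check on bleeding is kept.
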